2.4 Definitions

Baseline:

For participants with a combined Visit 1 and Visit 2, baseline refers to the combined visit (Day 0) when they were randomized. For participants with a separate Visit 1 and Visit 2, baseline refers to Visit 2 (Day 0) when they were randomized.

Study drug:

Study drug refers to the drug the participant was randomized to (either oral glutathione or placebo).

Treatment group:

Treatment group refers to participants randomized to either oral glutathione or placebo.

Follow-up time in weeks:

Follow up time in weeks will be calculated as the number of days from baseline to the final follow-up visit (approximately Week 24) or withdrawal date, divided by 7.

Follow-up time in months:

Follow up time in months will be calculated as the number of days from baseline to the final follow-up visit (approximately Week 24) or withdrawal date, divided by 30.4.

3. Overview of Planned Analyses

Unless otherwise noted, Poisson regression models with an offset for log of observation time will be used to derive rate ratios and corresponding 95% confidence intervals comparing treatment groups. Confidence intervals for differences in proportions between treatment groups will be calculated using the Newcombe-Wilson method without continuity correction and, where applicable, p-values for differences in proportions will be obtained from Fisher's exact tests.

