15 STATISTICAL METHODS AND CONSIDERATIONS

15.1 General Considerations

Prior to the analysis of the final study data, a detailed Statistical Analysis Plan (SAP) will be written, describing all analyses that will be performed. The SAP will contain any modifications to the analysis plan described below. All analyses will be performed using SAS® (SAS Institute, Inc., Cary, NC, USA) or R (R Foundation for Statistical Computing, Vienna, Austria).

For the purposes of analyses, baseline will be defined as Day 0 (Randomization/Visit 2). Except where otherwise noted, comparisons of continuous variables between treatment arms will utilize two-sample t-tests or multiple linear regression/ANOVA, proportions will be compared using Fisher's exact test, and rate ratios will be compared using Poisson regression. Except where otherwise noted, all tests will be two-sided and statistical significance will be determined at the 0.05 level. Missing data methods for the primary and key secondary endpoints will be described in the SAP. No adjustment for multiple comparisons will be made.

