15.4 Analysis of Secondary Endpoints

Descriptive analyses and graphical displays will be used to summarize all secondary endpoints. Endpoints will be compared between the GSH and placebo treatment groups from Visit 2 through Visit 4.

Continuous secondary endpoints which are collected at Visits 2, 3, and 4, including absolute changes and relative changes in weight, weight percentile, height, height-for-age z-score, height percentile, BMI, lung function (FEV₁ (liters and % predicted), FVC (liters and % predicted) and FEF₂₅₋₇₅ (liters/second and % predicted)), and fecal calprotectin, will be modeled using a linear mixed effects model similarly to the primary endpoint. The estimated treatment effect for the change for each secondary endpoint from Visit 2 to Visit 4 will be presented as well as corresponding 95% confidence intervals and p-values. Predicted values for spirometry measures at each visit will be calculated for those subjects ≥ 4 years of age at baseline using the Global Lung Initiative reference equations [33] Height for age z-score and height and weight percentiles will be calculated using the CDC reference equations [32].

Continuous measures collected only at Visit 2 and Visit 4, including neutrophil, platelets, and hs-CRP will be analyzed using ANOVA. The estimated treatment effect for the change for each secondary endpoint from Visit 2 to Visit 4 will be presented as well as corresponding 95% confidence intervals and p-values.

Event rates for hospitalization, PEs, intravenous antibiotic usage, inhaled antibiotic usage, and oral antibiotic usage from Visit 2 through Visit 4 will be descriptively summarized and differences in the proportions of subjects with an event between the treatment groups will be estimated with accompanying 95% confidence intervals. Event rates will be compared between treatment groups using Poisson regression.

Descriptive analyses will be used to summarize GI parent questionnaire data collected throughout the study. For each of the 14 gastrointestinal symptoms measured, changes from Visit 2 to Visit 4 will be summarized and compared between the GSH and placebo treatment groups.

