15.5 Analysis of Safety Endpoints

All reported treatment emergent SAEs and AEs will be coded using MedDRA and grouped by body system. Treatment emergent AEs are defined as AEs presenting post study treatment initiation. SAEs and AEs will be tabulated by treatment group using standard coding terms sorted by body system. The incidence of AEs in each treatment arm will be tabulated by severity.

The number of SAEs and AEs will be summarized for each treatment group as follows: (i) The proportion of subjects with at least one (S)AE, (ii) The average number of (S)AEs per patient, and (iii) The rate of (S)AEs per patient week of follow-up. Histograms showing the frequency of the number of (S)AEs in each treatment group will be included. Rates of (S)AEs by System Organ Class (SOC) will be presented by treatment group. Poisson regression modeling will be used to derive rate ratios and 95% CIs comparing overall S(AE) rates by treatment group as well as within each SOC. The rate ratios will be compared using a two-sided 0.05 level test for Poisson count data.

Safety lab data at Visit 2 and Visit 4 and changes from baseline will be summarized by treatment group. In addition, the following clinical laboratory summaries will be presented by treatment group: (i) the incidence of clinically significant abnormalities at each study visit; and (ii) tables summarizing the frequencies of subjects below, within, and above the normal reference ranges at baseline and end of study; and (iii) tables displaying baseline to end of study shifts in each laboratory value (shifts between below, within or above normal range).

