3.5 Adverse Events

Both the number of adverse events (AEs) and serious adverse events (SAEs) will be summarized by treatment group. The total number of (S)AEs, rate of (S)AEs per participant-month of follow-up, the average number of (S)AEs per participant, and the number of participants with at least one (S)AE will be provided. The number of (S)AEs per participant in each treatment group will be graphically represented as well as the proportion of participants in each treatment group experiencing at least one (S)AE by System Organ Class (SOC). Event counts and number of participants will be summarized for each SOC and (S)AE Preferred Term (PT) by treatment group, rates of (S)AEs by SOC will also be summarized. The number and percent of adverse events occurring will also be tabulated by severity.

The corresponding descriptive summaries and analyses are outlined in Appendix A, Section A.5 and a listing of serious adverse event narratives will be provided in Appendix B.

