3.6 Pulmonary Exacerbations, Hospitalizations, Antibiotic and Steroid Use

The number of events, rate per participant-month, and proportion of participants experiencing at least one event will be shown for pulmonary exacerbations (PEs) and hospitalizations. The distribution of number of PEs and hospitalization days will be summarized. Additionally, a listing of hospitalizations showing length of stay and indication will be included.

Proportions of participants initiating intravenous, inhaled, and oral antibiotics will be presented by treatment group along with summaries of the number of days of use (by route). The proportion of participants initiating steroids will be presented.

The corresponding summaries and analyses are outlined in Appendix A, Section A.6.

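### Event rate ratios come from Poisson regression with no stated allowance for overdispersion, so their 95% confidence intervals may be too narrow; a lesser point is that (S)AE person-time stops two weeks before (S)AE collection does

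*SAP*

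**What the plan says.** SAP section 3 (Overview of Planned Analyses) sets the default for rates, to apply unless something else is stated: "Poisson regression models with an offset for log of observation time will be used to derive rate ratios and corresponding 95% confidence intervals". SAP 3.5 and 3.6 state no exception. For adverse events, 3.5 lists the "rate of (S)AEs per participant-month of follow-up" among its summaries. For exacerbations and hospitalizations, 3.6 says: "The number of events, rate per participant-month, and proportion of participants experiencing at least one event will be shown". Both sections refer to Appendix A (A.5 and A.6) for detail; those pages are not in the supplied text.

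Protocol 15.4 covers hospitalizations, exacerbations and antibiotic use by route: "Event rates will be compared between treatment groups using Poisson regression". Protocol 15.5 derives Poisson rate ratios for (S)AEs overall and within each System Organ Class, then adds a test: "The rate ratios will be compared using a two-sided 0.05 level test for Poisson count data". The SAP does not repeat that test. Protocol 15.1 gives the SAP the last word: "The SAP will contain any modifications to the analysis plan described below".

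On person-time, SAP 2.4 says "Follow up time in months will be calculated as the number of days from baseline to the final follow-up visit (approximately Week 24"), or to withdrawal if that applies. On event collection, Protocol 9.1.13 captures AEs for the whole of participation, 11.2.1 runs SAE collection to the final visit or call, and 10.10 reviews AEs at Day 182 ± 14. The treatment-emergent definition has no end date: "Treatment emergent AEs are defined as AEs presenting post study treatment initiation".

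**The concern.** A Poisson model sets the variance of each child's count equal to its mean, which requires every child in an arm to share one underlying rate. That is a strong assumption here. The children are aged 2 to under 11, come from about 17 sites and differ in genotype, modulator use and lung function. AEs recur and are reviewed at seven scheduled contacts. The count model as described names no covariates, so differences between children remain as extra variance that the model does not count.

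At stake is the honesty of the intervals on secondary and safety rate ratios. An interval that is too narrow can suggest a difference in AE rates that is not there. It can also appear to exclude an excess that the data cannot exclude. The exacerbation rate is a named secondary endpoint and uses the same model.

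The person-time point is simpler: events between Visit 4 and the last contact enter the numerator of the (S)AE rate with no matching time in the denominator.

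**Working it through.** **The plan's own figure.** The plan gives no figure for the count analyses. Its one power statement (Protocol 15.9) fixes the arm size. With effect 0.36, SD 0.4, two-sided 0.05 and 90% power, n per arm = 2 × (1.960 + 1.282)² × 0.4² / 0.36² = 25.9, so 26 per arm or 52 in total. With the t distribution, 27 per arm gives power 0.901, which reproduces the stated 54. Then 54 / 0.9 = 60, or 30 per arm.

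**Assumptions.** The documents give neither event rates nor dispersion. I take 3 events per child, equal follow-up, a true rate ratio of 1, and φ = variance/mean of 1, 1.5, 2 and 3.

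**Formulas.** With event totals Y₁ and Y₀, the Poisson standard error of the log rate ratio is √(1/Y₁ + 1/Y₀); the true one is √φ times that. Hence:
- interval shortfall = 1 − 1/√φ
- real size of a nominal 0.05 test = 2 × [1 − Φ(1.96/√φ)]
- real coverage = 1 − size

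| φ | Shortfall | Size, formula | Size, simulated | Coverage, formula | Size, scaled model (simulated) |
|---|---|---|---|---|---|
| 1 | 0% | 5.0% | 4.9–5.0% | 95.0% | 3.8–3.9% |
| 1.5 | 18% | 11.0% | 10.5–10.9% | 89.0% | 4.8–4.9% |
| 2 | 29% | 16.6% | 16.4–16.5% | 83.4% | 5.0–5.1% |
| 3 | 42% | 25.8% | 25.3–25.7% | 74.2% | 4.9–5.3% |

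The simulated columns show the spread over separate runs of gamma-Poisson counts, 30 per arm. The scaled model uses a Pearson scale factor floored at 1 with t critical values on 58 degrees of freedom.

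**What this does to an interval.** With 90 events per arm (30 × 3) and an observed ratio of 1, the Poisson upper limit is exp(1.96 × √(2/90)) = 1.34. At φ = 2 it should be exp(1.96 × √2 × √(2/90)) = 1.51.

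**Less frequent counts.** At 0.2 events per child (6 expected per arm), simulated size is 4.0% at φ = 1.2 but about 7%, 8% to 9% and 11% at φ = 1.6, 1.8 and 2.2. A few children with repeated events would be enough.

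**Person-time.** At nominal days the uncounted time is 14/168 = 8.3% of the counted time. Keeping the planned two-week gap, it is 14/182 = 7.7% if Visit 4 falls on Day 182 and 14/154 = 9.1% if it falls on Day 154. All three assume a constant event rate to Week 26. For the rate ratio, let 20% of one arm and none of the other withdraw at Day 84: [(0.8 × 182 + 0.2 × 84) / (0.8 × 168 + 0.2 × 84)] / (182/168) = 1.0741 / 1.0833 = 0.991, a shift of 0.9%. Exacerbations, hospitalizations and antibiotics are defined from Visit 2 through Visit 4, so the mismatch does not touch them.

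**The case against.** The best case for the plan has four parts.

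- The omission is not proven. Section 3 is only a default, the detail may be in Appendix A.5 and A.6, and naming Poisson regression does not rule out a scale or robust-variance option. This stands: the point is that the supplied text leaves the variance method unstated, not that the sponsor has rejected one.
- The size of the harm is assumed. This also stands. The documents do not show that these counts are overdispersed, and at φ = 1 the planned method holds its level.
- A reader might infer that the trial's safety conclusions rest on a test with a false-positive rate of up to 26%. The documents do not support that. The test is in Protocol 15.5 only; SAP 3.5 lists counts, rates and proportions, and Protocol 15.1 lets the SAP change the plan. What certainly remains in the SAP is the interval, so coverage is the firmer measure.
- The proportions with at least one event, which overdispersion does not distort in this way, are planned for AEs, exacerbations and hospitalizations. This limits the damage without repairing the rate ratios.

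Two further inferences also fail. One is that rare events are immune; that holds at mild dispersion but not at the higher values shown above. The other is that the person-time mismatch biases the comparison of arms; it inflates both arms alike. The offset's observation time is also a different, undefined term and might already extend to Week 26. Events found off treatment, mostly by one telephone call, may be fewer, which would make the 8% smaller.

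**Conclusion.** The concern holds as a low-priority improvement to secondary and safety analyses. If recurrent counts are overdispersed, the stated method gives intervals that are too narrow: real coverage is about 89%, 84% and 74% at φ = 1.5, 2 and 3, with 3 events per child and 30 per arm. The Protocol 15.5 test, if it is kept, would run at about 11%, 16% and 26%. These figures depend on assumed rates and dispersion, and on Appendix A.5 and A.6 containing no adjustment.

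The person-time mismatch is minor: about 8% on absolute (S)AE rates if the event rate is constant to Week 26, and under 1% on the rate ratio.

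Nothing here touches the primary mixed-model analysis or the sample size. Nor should a reader extend it to the stopping rules, which the protocol frames around the primary endpoint.

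**What to change.** **SAP section 3.** State that all rate ratios and 95% intervals come from Poisson regression with the log-time offset, a Pearson scale factor floored at 1 and t critical values. A negative binomial model, or a robust variance with a small-sample correction, is acceptable if named in advance; without the correction, robust variance ran at about 6% to 7% for counts of 1 to 8 per child with φ of 1.5 to 3.

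Do not set an event-count threshold below which unscaled Poisson is kept. The documents give no basis for one. A threshold of 30 events, for example, would leave size at about 10.5% to 15.1% at 0.4 events per child and φ of 1.8 to 2.6. For sparse counts, rely mainly on the planned proportions with at least one event, with their Newcombe-Wilson intervals and, where applicable, Fisher's exact test.

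**SAP 2.4 and 3.5.** Define observation time. For (S)AE rates, run it from baseline to the last safety contact (the Week 26 call or Visit 5) or withdrawal. Keep Visit 2 to Visit 4 for exacerbations, hospitalizations and antibiotics.

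**Cost.** SAP wording and one model option.
- Frequent counts (3 per child) with no overdispersion: intervals about 6% wider; power at a true ratio of 1.5 falls from about 85% to 82%.
- Rare counts (0.2 per child in control, true ratio 3): the scaled test is conservative. Power falls from about 69% to 63% with no overdispersion, and from about 65% to 49% with a between-child frailty variance of 1. This is why the proportions should carry the sparse events.

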3.1 Enrollment and Withdrawal

Participant progress through the phases of the study (enrollment, treatment allocation, follow-up, and analyses populations) will be graphically displayed in a CONSORT diagram. The number of participants screened, eligible, randomized, treated, withdrawn, and completing the study during the randomized period will be summarized by both treatment group and site. Number of screening failures and reasons for failure will be summarized. Screening failures are participants that signed informed consent but did not meet eligibility criteria. The number of participants who withdrew early from the study will be tabulated by treatment group, reason for withdrawal and time to withdrawal will also be summarized.

The corresponding descriptive summaries are outlined in Appendix A, Section A.1.

3.2 Participant Demographics and Baseline Characteristics

Baseline demographics and clinical characteristics are descriptively summarized by treatment group and overall. Summarized characteristics include age, sex, CFTR genotype, race, height, weight, BMI, FEV₁ (liters and % predicted), fecal elastase, current chronic use of CFTR modulators, azithromycin, proton-pump inhibitors, H2 blockers as well as other chronic medications.

The corresponding descriptive summaries are outlined in Appendix A, Section A.2.

3.3 Protocol Adherence Measures

The number of participants expected to have completed each visit, the number of participants that did complete each visit, and the number of participants that missed each visit will be summarized by treatment group. The follow-up time in the randomized period is summarized overall and by treatment group and also as the average time for each participant.

The proportion of participants who discontinued study drug during the study will be shown by treatment group. Reasons for drug discontinuation and time to drug discontinuation will be also summarized.

Study drug compliance will be summarized by treatment group. Participants who discontinued study drug will be evaluated according to their assigned dose at randomization. Compliance percentage will be calculated for each participant as the number of doses reported taken divided by the number of doses expected, multiplied by 100. The average drug compliance will be summarized in each treatment group. Also shown is the number and percentage of participants with > 70% compliance. Mean compliance percentage and proportion of participants with > 70% compliance will be compared between treatment groups

A listing of all protocol violations will be provided. The number of participants included in the per-protocol population will be provided by treatment group and the reasons for exclusions will be listed. The per-protocol population is defined as all randomized participants having completed > 70% of doses of study drug (oral glutathione or placebo) and having incurred no major protocol violations.

The corresponding descriptive summaries are outlined in Appendix A, Section A.3.

3.4 Primary Endpoint

Weight-for-age z-score, the primary outcome measure, will be calculated using CDC reference equations based on age, sex, and weight. The number and percent of expected and observed measurements of weight-for-age z-score across visits will be tabulated by treatment group, along with reasons for missingness and the number and percent of participants with both baseline and end of study measurement.

The primary endpoint is the difference between the GSH and placebo groups in the change in weight-for-age z-score from Visit 2 (Baseline) to Visit 4 (Week 24). The difference between treatment groups will be estimated using a linear mixed effects model which will incorporate Visit 3 (Week 12) weight-for-age z-score measurements. The model will adjust for randomization strata, i.e., sex (male, female), baseline age (< 6 years, ≥ 6 years), baseline weight-for-age z-score category (< -0.52, ≥ -0.52), and historical fecal elastase (<200 µg/g, ≥200 µg/g, unavailable) and assume, if estimable, an unstructured covariance structure. Least squares mean changes at each visit and the estimated treatment differences with corresponding 95% confidence intervals from the model will be presented. The model-based p-value for the Visit 4 (Week 24) treatment difference will be evaluated against a two-sided 0.05 level of significance. Graphical displays will be used to show unadjusted mean changes in weight-for-age z-score across visits for the two treatment groups.

Sensitivity analyses of the primary endpoint will include:

- Performing the primary efficacy analysis on the per-protocol population.
- Performing the primary efficacy analysis on the sub population of subjects determined to be pancreatic insufficient (defined as fecal elastase < 200 µg/g).
- Least favorable treatment group imputation, which imputes missing values with the mean change from the treatment group with the worst change in the observed case analysis,

conservatively assuming that any participants who dropped out of the study had a less than favorable result.

Model-based mean changes in weight-for-age z-score from baseline to Visit 4 and treatment differences with corresponding 95% confidence intervals and p-values from the sensitivity analyses will be tabulated. The treatment difference for 24-week change in weight-for-age z-score and corresponding 95% confidence intervals based on the primary efficacy analysis as well as those from the sensitivity analyses will be graphical represented.

Subgroup analyses defined by baseline covariates will be performed, as subgroup size allows, using linear mixed models incorporating Visit 3 measurements without additional adjustment for randomization strata. Subgroups are as follows:

- Age (2-6 years, 6-10 years)
- Sex (Male, Female)
- CF Genotype (F508 del Homozygous, F508 Heterozygous, Other)
- Height Percentile (< 50th Percentile, ≥ 50th Percentile)
- Weight Percentile (< 30th Percentile, ≥ 30th Percentile)
- FEV₁ percent of predicted (< 90%, ≥90%)
- Fecal Elastase (< 100 µg/g, ≥ 100 µg/g)
- CFTR Modulator Use (Yes, No)
- Use of Appetite Stimulants (Yes, No)
- Use of Nutritional Supplements (Yes, No)
- G-tube (Yes, No)

Model-based mean changes in weight-for-age z-score from baseline to Visit 4 and treatment differences with corresponding 95% confidence intervals and p-values from the subgroup analyses will be shown. The treatment difference for Visit 4 weight-for-age z-score and corresponding 95% confidence intervals based on the subgroup analyses will be graphically represented.

Summary statistics will be tabulated by treatment group for weight-for-age z-score at baseline, Week 12, and Week 24. Both absolute and relative changes from baseline will be presented for Week 12 and Week 24. Treatment differences and corresponding 95% confidence intervals will be provided for the Week 24 absolute and relative changes. Figures displaying mean values and mean changes from baseline by treatment group across visits will be provided for each anthropometric endpoint.

Individual weight-for-age z-scores trajectories will be plotted across study visits by treatment group.

The corresponding descriptive summaries are outlined in Appendix A, Section A.4.

